5.1 Adherence

Adherence was monitored through a self-reported receipt of the school meals during a reference week. Adherence will not be defined as receiving the school meals five times during the reference week (once per day).

5.2 Protocol deviations

No protocol deviations were reported during the trial.

5.3 Definition of analysis sample

The sample will be analysed using an intention-to-treat approach.

6. Outcome variables

6.1 Data collection procedures

Data were collected using quantitative household questionnaires administered to the child and primary caregiver.

6.2 Outcome variable definitions

- Diet diversity score in children will be measured using the Minimum dietary diversity for women (MDD-W) guidelines at baseline and endline. We will calculate a count score, summing 10 foods groups, and a binary indicator for consuming ≥5 food groups in the previous 24h. Milk consumption will be calculated using self-reported consumption in the previous 24h.
- Cognition in children will be measured using the forward and backward digit span and the standard progressive matrices at baseline and endline. We will calculate raw scores summing the correct responses to each module. We will also calculate standardized scores, standardized within the sample. If age and sex distributions allow, we will calculate age and sex standardized scores. We will also use structural equation modeling to examine cognition as a latent construct.
- Learning in children will be measured using literacy and numeracy scores at baseline and endline. We will calculate raw scores by summing the correct responses to each set of questions. We will also calculate standardized scores, standardized within the sample. If age and sex distributions allow, we will calculate age and sex standardized scores.
- Nutritional status will be measured using body mass index Z-score (BMIZ) and height-for-age Z-score (HAZ) at baseline and endline. BMIZ and HAZ will be calculated using the WHO 2007 Growth Reference (2). Stunting will be defined as HAZ <-2. Thinness will be defined as BMIZ <-2. Overweight will be defined as BMIZ as >1 and obesity as BMIZ >2 (2).
- School attendance will be measured using school observations at baseline and endline. We will calculate the total number of students present on the day of the visit.
- Perceptions of the school feeding program will be measured using caregiver self-report at baseline and endline. Binary indicators will be created for different variables to show the proportion of caregivers with a perception.
- Child health will be measured using caregiver report of child morbidity symptoms at baseline and endline. We will create binary indicators for each symptom experienced. We will also calculate a summary indicator for the total number of symptoms experienced.

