3.1 Trial design

In this cluster randomized controlled effectiveness trial, 42 schools in Al Mhuka district, Taiz Governorate, Yemen were randomly assigned to one of two groups: (1) Standard of care (control) group, which WFP's school feeding program involving daily distribution of high energy biscuits (n=20); and (2) School milk (intervention) group, which received the standard of care intervention with the addition of a daily drink of milk. A baseline survey was conducted prior to the start of the milk distribution in November 2023. An endline survey was conducted at the end of the school year in May 2024.

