3.2 Recruitment

The primary reference group for this study is primary school aged children enrolled in schools supported by the school feeding program. A secondary reference group includes their caregivers. Lists of currently enrolled children were obtained from each school at the start of the school year. Children were randomly selected for participation in the survey, where the selection was stratified by gender.

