6.3 Primary outcome

Individual daily diet diversity and milk consumption are the primary outcomes¹. Cognition, learning, nutritional status, attendance, perceptions, and health are secondary outcomes.

¹ There was an inconsistency with pre-specified primary research question (including both dietary diversity and nutritious food consumption) and primary outcome specification in trial registration (only including dietary diversity). This wording resolves consistency and aligns with primary research question.

7. Covariates and interaction terms

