8.3 Statistical analysis plan for each hypothesis

We will a single difference model specification of the following form:

$$Y_{i1} = \beta_0 + \beta_1 T_i + \beta_2 Y_{i0} + \varepsilon_i$$

where Y_{i0} is the outcome variable at baseline, Y_{i1} is the outcome variable at endline and T_i is a dummy variable for the treatment. This (ANCOVA) estimator has been shown to provide more efficient estimates of program impact than difference-in-difference estimators when autocorrelation of outcomes is low (4). To account for c-RCT design and the level of clustering of the outcome under analysis, we will employ linear multi-level regression models. The multi-level models will use both fixed effects with dummy variables for each intervention and random effects at the school level (unit of randomisation) to take into account clustering and to estimate the standard error in an unbiased manner. Alternative fixed effect models with standard errors clustered at the school level will also be considered. Primary analyses will be unadjusted for baseline covariates. In addition to the unadjusted primary analyses, we will report adjusted estimates, conditional on the covariates described in 7.2 above. We will use linear multi-level regression models and estimate mean differences for continuous outcomes and risk differences for binary outcomes. Alternative log-binomial and log-Poisson models will be considered for binary outcomes.

The same model will be repeated with the addition of an interaction term to assess effect modification for the variables listed in 7.3 above.

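### Attendance (secondary) is a raw head-count without an enrolment denominator, and section 8.3 gives no school-level analysis suited to it

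*SAP*

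**What the plan says.** SAP 6.2 on the data source: "School attendance will be measured using school observations at baseline and endline". On the variable: "We will calculate the total number of students present on the day of the visit". Nothing else in the SAP defines attendance: there is no proportion, offset or per-child indicator.

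SAP 6.3 gives its status: "Cognition, learning, nutritional status, attendance, perceptions, and health are secondary outcomes".

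SAP 8.3 sets out one specification for all outcomes, an ANCOVA of the endline value on treatment and the baseline value of the same outcome. For it "we will employ linear multi-level regression models", with "random effects at the school level (unit of randomisation) to take into account clustering". Alternatives with standard errors clustered by school are to be considered, but none is tied to attendance. The covariates of 7.2 and the effect modifiers of 7.3 describe the child, caregiver or household. Enrolment and school size are not among them.

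Enrolment was known at the start. SAP 3.2: "Lists of currently enrolled children were obtained from each school at the start of the school year". SAP 3.4 used enrolment data to form the size tertiles within which schools were randomised.

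**The concern.** A head-count is enrolment multiplied by the attendance rate. Without a denominator, the treatment effect is a difference in pupils present per school, and three things follow.

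- The same gain in the attendance rate gives a larger number in a larger school, so large schools dominate the mean difference.
- A change in enrolment between the November 2023 and May 2024 surveys is read as a change in attendance. School milk might itself attract enrolment.
- Variation in school size and in enrolment change adds noise that a rate would not carry.

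The general model of 8.3 is also written for children nested in schools. A school total, taken once per survey round, has no within-school replication and no child-level covariates. If the denominator and model are chosen after the data are seen, the attendance result is open to selective reporting.

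**Working it through.** **The plan's own figure.** The SAP gives no power figure for attendance. Its only calculation (3.5) is a minimum detectable effect of 0.26 SD for dietary diversity. It reproduces: design effect 1 + 29 × 0.05 = 2.45, and (t₀.₉₇₅,₃₈ + t₀.₈₀,₃₈) × √(2.45/30 × (1/20 + 1/20)) = 0.260 at an assumed 80% power. It has no bearing on attendance.

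**1. Does school size bias the contrast?** No. In simulations of 42 schools randomised within size tertiles, with no effect on rate or enrolment, the head-count ANCOVA was unbiased and rejected in about 3-5% of trials.

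**2. Effect measure.** A 6-point gain is 0.06 × 100 = 6 pupils in a school of 100 and 0.06 × 400 = 24 in a school of 400 (illustrative sizes).

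**3. Enrolment change.** Assume mean enrolment 250, attendance 70%, no effect on the rate and 10% higher enrolment in the milk arm. The expected head-count effect is 0.10 × 250 × 0.70 = 17.5 pupils per school. Simulation gave +17 to +18 pupils with rejection in 20-46% of trials. The rate on current enrolment gave about 0, with rejection in 4-7%. A rate on start-of-year enrolment would not remove the problem: it would show 0.10 × 0.70 = 7 percentage points.

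**4. Precision.** All inputs are assumptions, since the SAP gives none: 42 schools, mean enrolment 250, size CV 0.4 or 0.7, attendance 75%, gain 6 points, and between-school and day-to-day SD of the rate 6 points each. The SE is the residual SD × √(4/42) = residual SD × 0.309; the critical t on 39 df is 2.02.

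- *Rate.* Variance 0.0036 + 0.0036 = 0.0072; baseline-endline correlation 0.5; residual variance 0.0072 × (1 − 0.25) = 0.0054. SE 0.0735 × 0.309 = 0.0227; 0.06/0.0227 = 2.65; power about 73%.
- *Head-count, no drift.* With a baseline slope near 1, residual variance ≈ 250² × (1 + CV²) × 0.0072, which is 522 (CV 0.4) or 670 (CV 0.7). SE 7.05 or 7.99. The effect is 0.06 × 250 = 15 pupils, so the ratios are 2.13 and 1.88; power about 55% and 45%.
- *Head-count, 10% (SD) enrolment drift.* Replace 0.0072 by 0.0072 + 0.75² × 0.01 = 0.0128. SE 9.41 or 10.67; power about 34% and 28%.
- *Rate on start-of-year enrolment, same drift.* Residual variance 0.0054 + 0.0056 = 0.0110; SE 0.0324; ratio 1.85; power about 43-44%.

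Simulations on these inputs agree: head-count 45-55% against 73% without drift; with drift, 27-34% for the head-count, 41% with start-of-year enrolment and 71-73% with a current register. Adding binomial variation between pupils lowers the rate's power to about 64-65% without drift. A second set of assumptions (8-point gain, attendance 70%, SD of the rate 10 points, CV 0.4 to 1.0) gave 44-60% against 73-77%.

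**5. Random effect.** With one endline value per school, the likelihood depends only on the sum σ²(school) + σ²(residual). In an illustrative 42-school data set the log-likelihood was −185.228 whether 0%, 25%, 50% or 90% of the variance was assigned to the school. The split is not identified. The treatment coefficient is, and the model reduces to a 42-point ANCOVA.

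**The case against.** The case for leaving the plan alone has real substance.

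- *School size is handled by design.* A reader might infer that the estimate is confounded by school size. It is not: stratification by tertile and the baseline-count term deal with stable size differences.
- *The model still works.* A reader might infer that the model of 8.3 cannot be fitted. Only the variance split is lost. The treatment effect remains estimable, and the reference in 8.3 to the level of clustering of each outcome leaves room for a school-level fit. One count per school is also inferred; the SAP does not say whether counts are taken by class or grade.
- *Covariates are secondary.* The primary analyses in 8.3 are unadjusted for baseline covariates, so the main attendance estimate does not need them.
- *A rate is not always more powerful.* If milk raised attendance by 6 points and enrolment by 5%, with no drift, simulated power was 82-89% for the head-count against 64-65% for the rate. The two measures target different effects.
- *The better denominator may not exist.* The SAP documents enrolment at the start of the year only. An endline register is also post-randomisation: if milk attracts pupils, the enrolled populations differ between arms.

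All of this stands, and it limits the point. It does not supply a denominator, or say which effect the attendance outcome is meant to measure. The general wording in 8.3 fixes no analysis for a school-level count.

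**Conclusion.** The definition should be changed, but the harm is bounded. As written, the attendance result is a pupils-per-school difference that depends on school size and merges enrolment change with attendance. It is less precise than a rate when the rate changes and enrolment does not: about 45-55% power against 73% without drift. Those figures are illustrative and rest wholly on the assumed enrolment, attendance and variance inputs.

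If there is one count per school, the school and residual variances in 8.3 cannot be separated, and the child-level adjusted and interaction models have no meaning for this outcome. The documents support neither bias from stable school size nor a model that fails to estimate the treatment effect. Nor do they show that every datum for the best rate was collected. Attendance is one of six secondary domains and the primary outcomes are unaffected, so this is a should-fix.

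**What to change.** In 6.2, define attendance as pupils present divided by pupils enrolled at that school.

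- *Denominator.* Use the register at the time of each visit if it was recorded, and note that at endline this denominator is post-randomisation. Otherwise use the documented start-of-year enrolment, and state that enrolment change then remains in the measure.
- *Model.* In 8.3, add a school-level analysis with one row per school (n = 42): endline rate on arm, baseline rate and size tertile, with t-based inference on the residual degrees of freedom.
- *Supplementary result.* Report the head-count alongside, described as pupils present per school.
- *Exclusions.* State that attendance is left out of the child-level adjusted models (7.2) and the interaction models (7.3).

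The cost is a few sentences in the SAP and one school-level regression. With start-of-year enrolment no new data are needed. Whether endline enrolment was recorded has to be checked, because the SAP does not say.

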6.3 Primary outcome

Individual daily diet diversity and milk consumption are the primary outcomes¹. Cognition, learning, nutritional status, attendance, perceptions, and health are secondary outcomes.

¹ There was an inconsistency with pre-specified primary research question (including both dietary diversity and nutritious food consumption) and primary outcome specification in trial registration (only including dietary diversity). This wording resolves consistency and aligns with primary research question.

7. Covariates and interaction terms

7.1 Data collection procedures

Data were collected using quantitative household questionnaires administered to the child and primary caregiver.

7.2 Covariate variable definitions

Adjusted analyses will control for the following confounders, all of which were selected a priori. Covariates will be defined the same way as described in section 4.1

Variable	Definition
Child age	Age in years
Child sex	Male vs female
Child grade	Current grade in school
Caregiver age	Age in years of primary caregiver
Caregiver education	Level of education of primary caregiver: no formal education complete, primary complete, secondary complete, higher complete. Depending on the distribution we will also create an indicator for any formal education vs none.
Household head age	Age in years of head of household
Household head occupation	Primary occupation of the head of household
Household wealth	Wealth quintile, derived from a wealth index, which will be derived hosing
quintile	characteristics and asset ownership using Principal Components Analysis
Household size	Total number of household members

7.3 Effect modification testing or subgroup analysis

Effect modification will be assessed by interacting treatment assignment with the following potential effect modifiers, selected a priori: child sex (male vs female), child age (continuous, categorical for each of the following groups 6-9, 10-14, 15-18 y), caregiver age (continuous, categorical for <20, 20-29, 30-39, 40-49, etc depending on the distribution, caregiver education (any formal vs none, to increase power), and household wealth (bottom two vs top three, to increase power). Effect modification will be considered significant at p<0.10.

8. Statistical analysis

8.1 Framework, confidence intervals and p-values

All tests will be two-sided, at 95% confidence interval and a 5% significance level unless otherwise indicated (i.e., interaction analyses). No adjustments will be made for multiple hypothesis testing (3).

8.2 Missing data

Missing data on any covariates will be imputed using mean cluster imputation if <5% of data is missing and multiple imputation if $\ge5\%$ of missingness. Missing data on outcomes will not be imputed.

8.3 Statistical analysis plan for each hypothesis

We will a single difference model specification of the following form:

$$Y_{i1} = \beta_0 + \beta_1 T_i + \beta_2 Y_{i0} + \varepsilon_i$$

where Y_{i0} is the outcome variable at baseline, Y_{i1} is the outcome variable at endline and T_i is a dummy variable for the treatment. This (ANCOVA) estimator has been shown to provide more efficient estimates of program impact than difference-in-difference estimators when autocorrelation of outcomes is low (4). To account for c-RCT design and the level of clustering of the outcome under analysis, we will employ linear multi-level regression models. The multi-level models will use both fixed effects with dummy variables for each intervention and random effects at the school level (unit of randomisation) to take into account clustering and to estimate the standard error in an unbiased manner. Alternative fixed effect models with standard errors clustered at the school level will also be considered. Primary analyses will be unadjusted for baseline covariates. In addition to the unadjusted primary analyses, we will report adjusted estimates, conditional on the covariates described in 7.2 above. We will use linear multi-level regression models and estimate mean differences for continuous outcomes and risk differences for binary outcomes. Alternative log-binomial and log-Poisson models will be considered for binary outcomes.

The same model will be repeated with the addition of an interaction term to assess effect modification for the variables listed in 7.3 above.

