3.4 Randomization

A list including 42 eligible schools in the targeted districts was obtained from the Ministry of Education by in-country implementation partners. Data on school enrolment was used to classify the targeted schools into tertiles of school size. The 42 schools (clusters) were then allocated to the two study groups using a simple randomisation procedure performed in Stata, with randomisation stratified by school size tertile. The original intent of using restricted randomisation to allocate schools to interventions was abandoned due to the unavailability of school level data prior to the baseline and the need to allow implementers to plan for implementation roll-out as soon as the baseline survey was completed.

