3.5 Sample size, power, and detectable difference

Power calculations based on available clusters in targeted districts and resource availability suggested 20 clusters (schools) per intervention arm and 30 households (with index children) per cluster. The primary outcomes of the trial include the 10-food group dietary diversity score in primary school children. For this outcome, assuming an inter cluster correlation coefficient (ICC) of 0.05, a sample size of 30 children per school leads to a minimum detectable effect size (MDES) of 0.26 SDs.

4. Sample characteristics

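### Randomisation was stratified by school-size tertile, but no planned model includes tertile; depending on how allocation was done, this may cost precision and make the test conservative

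*SAP*

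**What the plan says.** Section 3.4 classifies the schools by enrolment into tertiles and reports allocation "using a simple randomisation procedure performed in Stata, with randomisation stratified by school size tertile". It gives no block size and no rule for balance within a tertile. It also says that a planned restricted randomisation was dropped, so the tertile strata are the only balancing device left in the design.

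Section 8.3 regresses the endline outcome on treatment and the baseline value, with a random effect for school, and adds: "Primary analyses will be unadjusted for baseline covariates". The alternatives it mentions (school-clustered standard errors, log-binomial and log-Poisson models) bring in no stratum term. The adjusted model takes its covariates from section 7.2, which lists child, caregiver and household characteristics only. School size appears in neither model.

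**The concern.** Stratified allocation removes some between-stratum variation from the treatment comparison. If the model ignores the strata, that variation stays in the school-level residual variance. The reported standard error then describes a less well-balanced trial than the one that was run. Section 8.3 justifies the multilevel model by the wish for an unbiased standard error, so leaving out a prognostic stratum can defeat the plan's own purpose.

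At stake is precision in a trial whose information is limited by 42 schools. For one secondary outcome the link with size is plain: attendance is a count of pupils present (section 6.2), which depends on how large the school is, although the baseline count will absorb part of this.

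**Working it through.** **Inputs.** From the SAP: 42 schools (3.4), 20 of them control (3.1); 30 children per school and ICC 0.05 (3.5); two-sided 5% (8.1). By inference: 22 intervention schools by subtraction, and 14 schools per tertile if the tertiles are equal. By assumption: 80% power, because 3.5 states none; and the share R of between-school variance explained by tertile, taken as 0, 10, 25 and 50%, because the SAP gives no figure. Outcomes are in SD units. The baseline-outcome term is ignored, so R should be read as the share left after baseline adjustment.

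**Step 1: the plan's own figure.** Section 3.5 uses "20 clusters (schools) per intervention arm and 30 households (with index children) per cluster" and reports a "minimum detectable effect size (MDES) of 0.26 SDs".
- Design effect = 1 + 29 × 0.05 = 2.45.
- SE = √[2.45/30 × (1/20 + 1/20)] = 0.0904.
- Detectable effect on 38 df = (2.024 + 0.851) × 0.0904 = 0.260. The figure reproduces at 80% power.

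**Step 2: SE with a tertile term, 20 v 22 schools.** The variance of a school mean is 0.05(1 − R) + 0.95/30, and SE = √[that × (1/20 + 1/22)]. Without the term the SE stays at about 0.088.

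| R | SE with term | 0.0883 ÷ SE | Detectable effect (38 df) |
|---|---|---|---|
| 0 | 0.0883 | 1.00 | 0.254 |
| 10% | 0.0855 | 1.03 | 0.246 |
| 25% | 0.0813 | 1.09 | 0.234 |
| 50% | 0.0735 | 1.20 | 0.212 |

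**Step 3: does the model without tertile report the right SE?** This depends on the allocation. For each row below, 20,000 sets of 42 school means were simulated and analysed with and without two tertile indicators, using t reference distributions. Monte Carlo error on a 5% rate is √(0.05 × 0.95/20,000) = 0.15 percentage points.

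| Allocation (intervention:control) | R | Model SE ÷ true SD, no term | Type I error, no term | Power at 0.26 SD, no term | Power, with term |
|---|---|---|---|---|---|
| 7:7 in each tertile | 0 | 1.002 | 5.0% | 82.4% | 82.3% |
| | 10% | 1.033 | 4.3% | 82.7% | 84.0% |
| | 25% | 1.083 | 3.5% | 84.0% | 87.9% |
| | 50% | 1.205 | 1.9% | 85.6% | 92.9% |
| 8:6, 7:7, 7:7 | 0 | 0.999 | 5.1% | 81.8% | 81.7% |
| | 10% | 1.028 | 4.3% | 82.3% | 83.9% |
| | 25% | 1.072 | 3.6% | 83.6% | 87.7% |
| | 50% | 1.191 | 2.1% | 85.3% | 93.0% |
| 22 of 42, tertile not balanced | 0 | 0.999 | 4.9% | 81.6% | 79.8% |
| | 10% | 1.001 | 4.8% | 82.0% | 82.4% |
| | 25% | 1.001 | 5.1% | 81.6% | 85.6% |
| | 50% | 0.999 | 5.2% | 81.5% | 91.8% |

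An independent coin toss for each school gives the same pattern as the last block (SE ratio 0.99 to 1.00).

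**Step 4: size imbalance left in the estimate.** With a linear trend across tertiles, the outer tertiles sit at ±√(1.5 × 0.05 × R). An 8:6 split in one outer tertile shifts the estimate by √(1.5 × 0.05 × R) × (1/20 + 1/22), which is 0.008, 0.013 and 0.018 SD at R = 10, 25 and 50%. A split with 10, 7 and 5 intervention schools shifts it by five times as much: 0.041, 0.065 and 0.092 SD.

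**The case against.** The strongest reply is that the SAP does not establish that anything is lost. Section 3.4 calls the procedure simple as well as stratified. If there was no balance within tertiles, the planned standard error is correct, as the last block of the Step 3 table shows. The SAP also gives no evidence that tertile predicts diet diversity or milk consumption once baseline is in the model. Both points stand, and they are why the consequence is conditional.

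A reader might infer that standard errors are certainly too large and that a size imbalance also contaminates the estimate. The documents do not support both at once, because the two are largely alternatives. Near-balance inflates the SE but leaves a shift of at most about 0.02 SD in the near-balanced case tried. Unbalanced allocation can leave more, but the SE then covers it. It is chance imbalance, not bias. Nor is it established that the tertiles could not all be split 7:7: tertiles of 14 and 22 intervention schools are inferences, and the 20 in section 3.1 could echo the 20 per arm planned in section 3.5.

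The size of any conservatism also depends on the reference distribution, which section 8.3 does not fix for the multilevel model. With a normal reference and near-balanced 20:22 allocation, type I error is about 5.2% at a 10% share and 4.4% at 20%. So a flat statement that type I error falls below 5% can fail at modest shares.

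Finally, the sentence quoted from section 8.3 concerns covariates in general. The omission shows only when the model equation is read with section 3.4. None of this supplies a reason for leaving the stratification factor out.

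**Conclusion.** The omission is a fact of the document: the strata used to allocate schools appear in no planned model. Its effect is moderate and depends on two things that the SAP does not settle.

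- **Tertile prognostic, allocation balanced or nearly so:** the SE is about 3 to 8% too large at shares of 10 to 25%, and power at 0.26 SD is about 82 to 84% instead of 84 to 88%.
- **Tertile prognostic, allocation not balanced within tertiles:** the SE is about right, but power that the term would recover is lost (81.6% against 85.6% at a 25% share), and a chance size imbalance stays unadjusted.
- **Tertile not prognostic:** omission loses nothing.

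These sizes rest on assumed shares, ICC 0.05, 30 children in every school and no credit for the baseline term. The error, where it exists, costs power and does not threaten validity. The absence of a school-level baseline mean from the model is not part of this error. The change should be made, but a trial analysed without it would not be invalid.

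**What to change.** In section 8.3, add two indicator variables for school-size tertile as fixed effects to all primary, secondary and adjusted models. Define the unadjusted analysis as one with no covariates other than the baseline outcome and the stratification factor. In section 3.4, state whether allocation was balanced within tertiles, and give the number of schools per arm in each.

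The cost is SAP wording and two school-level degrees of freedom (40 down to 38). Tertile is already known for every school, so nothing new is collected and no values are missing. If tertile turns out not to be prognostic, the simulated power cost is about 0.1 percentage points under balanced or near-balanced allocation and about 2 points without balance. Since the SAP describes the endline survey as already done, the change should be dated in section 9, with the model without tertile reported alongside. Adding the school mean of the baseline outcome is optional.

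### Binary-outcome interaction tests rest on a linear model with one residual variance; school-clustered standard errors should be the rule for them, not an option

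*SAP*

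**What the plan says.** Section 8.3 of the SAP names one main model for both types of outcome: "We will use linear multi-level regression models and estimate mean differences for continuous outcomes and risk differences for binary outcomes". The standard error comes from "random effects at the school level (unit of randomisation) to take into account clustering and to estimate the standard error in an unbiased manner". No robust variance is named for this model.

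Effect modification uses the same machinery: "The same model will be repeated with the addition of an interaction term to assess effect modification". Section 7.3 sets the threshold: "Effect modification will be considered significant at p<0.10". Its modifiers are child sex, child age (continuous and in bands 6-9, 10-14 and 15-18 y), caregiver age, caregiver education (any formal v none) and household wealth (bottom two v top three quintiles). Section 8.1 makes no adjustment for multiple testing.

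Section 6.2 defines many binary outcomes, among them "a binary indicator for consuming ≥5 food groups in the previous 24h", stunting, thinness, overweight, each morbidity symptom and each caregiver perception.

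Two alternatives are mentioned in 8.3: "Alternative fixed effect models with standard errors clustered at the school level will also be considered", and "Alternative log-binomial and log-Poisson models will be considered for binary outcomes". Neither comes with a rule for when it applies or which result prevails.

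**The concern.** A school random effect deals with correlation between children in the same school. It does not deal with a residual variance that differs between groups of children. For a 0/1 outcome the variance is p(1-p), so it changes whenever risk moves nearer to or further from 50%.

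The variance of a treatment-by-modifier contrast comes mostly from the smaller modifier group. The linear model gives that group a pooled variance, which is dominated by the larger group. If the two groups differ in p(1-p), the standard error is off, and the claim in 8.3 that it is estimated without bias fails for these tests. This happens even when the modifier acts identically in every school.

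At stake is the meaning of p<0.10 for subgroup claims on binary outcomes. In one direction false modifiers are declared too often. In the other the intervals are too wide and real ones are missed. With no multiplicity adjustment, each test's own error rate is the only control.

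**Working it through.** **Design inputs from the SAP.** Section 8.1: two-sided tests. Section 7.3: 10% level for interactions. Section 3.1: 42 schools, 20 of them control, hence 22 in the milk arm. Section 3.5: 30 children per school, ICC 0.05.

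**The plan's own figure first.** Section 3.5 gives a minimum detectable effect of 0.26 SD for 20 schools per arm. The design effect is 1 + 29 × 0.05 = 2.45. With 600 children per arm the standard error is sqrt(2.45 × 2/600) = 0.0904 SD. Taking 80% power (an assumption, since the SAP states none) and t on 38 df, (2.024 + 0.851) × 0.0904 = 0.26. The figure reproduces, so the same design inputs are used below.

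**Assumed inputs.** The SAP gives no subgroup risks, and no subgroup shares beyond the 40/60 implied by the wealth quintiles. Let f be the share of the smaller group, v_s its p(1-p), and v_l that of the larger group.

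**Formula.** With nearly equal arms and no true interaction, the ratio of true to model-based variance is

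R = [v_s/f + v_l/(1-f)] / {[f·v_s + (1-f)·v_l] × [1/f + 1/(1-f)]},

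and the actual size of the nominal 10% test is 2 × [1 - Φ(1.645/√R)].

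**Example, f = 0.2, 40% in the smaller group v 15%.** v_s = 0.24 and v_l = 0.1275. The numerator is 1.2 + 0.1594 = 1.3594 and the denominator is 0.15 × 6.25 = 0.9375. R = 1.45 and the size is 17.2%.

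**Reverse direction, f = 0.2, 10% v 35%.** v_s = 0.09 and v_l = 0.2275. The numerator is 0.45 + 0.2844 = 0.7344 and the denominator is 0.20 × 6.25 = 1.25. R = 0.59 and the size is 3.2%.

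| Share of smaller group | Risk, smaller v larger | R | Actual size |
|---|---|---|---|
| 20% | 40% v 15% | 1.45 | 17.2% |
| 20% | 10% v 35% | 0.59 | 3.2% |
| 20% | 30% v 20% | 1.18 | 12.9% |
| 20% | 20% v 30% | 0.85 | 7.4% |
| 20% | 60% v 40% | 1.00 | 10.0% |
| 40% (wealth) | 40% v 15% | 1.13 | 12.2% |
| 40% (wealth) | 10% v 35% | 0.84 | 7.3% |
| 50% | any | 1.00 | 10.0% |

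The 10-point-gap range is quoted elsewhere as about 7% to 14%, rounded outward because simulated sizes scatter by about a percentage point around the formula.

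**Check on the absolute scale.** With 600 and 660 children per arm and f = 0.2, the four cells hold 120, 480, 132 and 528 children.
- 40% v 15%: true variance 0.24 × (1/120 + 1/132) + 0.1275 × (1/480 + 1/528) = 0.00433, SD 0.066. Model variance 0.15 × 0.01989 = 0.00298, SE 0.055.
- 10% v 35%: true SD 0.048, model SE 0.063.

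**Simulation.** The set-up was a random-intercept linear model with the baseline outcome included, 20 + 22 schools of 30, ICC 0.05, f = 0.2 and 3,000 runs.
- 40% v 15%: model SE 0.054 against a true SD of 0.066; rejection 17.8%. School-clustered errors with t on 40 df: 10.4%.
- 10% v 35%: model SE 0.063 against a true SD of 0.049; rejection 2.9%. Clustered: 10.1%.
- 30% v 30%: rejection 9.6% with the model-based error.

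Other simulations of these two unequal cases gave about 17% and 4% with model-based errors, and about 11% in both with clustered errors. Across 18 scenarios of varying share and risk, clustered errors ran at 10.1% to 11.8%, against 1.8% to 28.0% with model-based errors. One further set of runs put clustered errors at up to 12% to 14% in some cases.

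**Main effect.** The same reasoning applied to the two arms gives almost no distortion, because 20 v 22 schools is nearly balanced.

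**The case against.** The best defence is that the SAP already names school-clustered errors, and log-binomial or log-Poisson models for binary outcomes. That is true, and clustered errors do restore the size. But they are attached to an alternative model and are only to be considered, so the standard error could be chosen after the results are seen. Log-link models would usually test interaction on a ratio scale, which is a different question from a difference in risk differences.

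A second objection is scope, and it largely stands. Selection was stratified by gender (section 3.2), so the sex split is probably near 50/50 and its test stays at about 10%. Wealth is fixed at 40/60 and drifts only to about 7% to 12% at the risks used above. Only a lopsided split with a clear gap in p(1-p) produces large errors. Education and the age bands could be like that, but the SAP does not show that they are. The calculations cover two-group modifiers, not three bands or continuous age.

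Three stronger readings are tempting, and the SAP supports none of them:
- **That the plan's 10% threshold runs at some fixed wrong rate, such as 4% to 19%.** That range matches, for example, a 25% subgroup with risks of 10% v 40% (3.8% to 19.2%). These inputs are assumed. Others give about 10%, or values outside the range.
- **That the higher-risk group decides the direction.** It is p(1-p) that decides. At 60% v 40% nothing happens, and when both risks exceed 50% the pattern reverses.
- **That the overall risk differences are compromised.** They are not, because the arms are nearly equal.

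**Conclusion.** The concern holds in conditional form. The SAP fixes a model-based standard error that is correct for binary-outcome interactions only if the modifier groups are of about equal size or have about equal p(1-p). It does not commit to the remedy that it mentions.

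For a 20% subgroup in 42 schools of 30 with ICC about 0.05, the nominal 10% test runs at about 17% (40% v 15%) or about 3% to 4% (10% v 35%). It runs at about 7% to 14% for a 10-point gap between 20% and 30%, and at about 10% when groups or variances are equal. The subgroup shares and risks are assumptions throughout.

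The consequence is confined to the effect-modification analyses of binary outcomes. It is worth correcting because the correction is nearly free, but it does not threaten the trial's main comparison.

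**What to change.** In section 8.3, state that linear multi-level models of binary outcomes are reported with school-clustered robust standard errors and a t reference on about 40 df (42 schools less 2), and that the section 7.3 interaction tests on binary outcomes use these errors. Delete the wording that leaves clustering to be considered, at least for these tests. Keep the risk-difference estimates as planned.

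The cost is one or two sentences in the SAP and a small change to the analysis code. No new data are needed.

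The downside is that with 42 schools the clustered test stays slightly liberal: about 10% to 12% in most cases tried, and up to 14% in a few. A small-sample correction such as CR2 with Satterthwaite df may be added. It was not tested here and may take more than a single command option.
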